2. STUDY OBJECTIVES, DURATION, AND STUDY SITES

2.1. Study Objectives

Objective 1: *Collect baseline data during the first 6 months before implementing any intervention component.*

Objective 2: *Implement the intervention in three phases: 1) provider education plus community outreach; 2) add provider assessment and feedback + patient reminder; and 3) add a CRC navigator program.*

Objective 3: *Create a grand model to test the overall effectiveness of the multilevel intervention on primary outcomes within and across levels, as well as separate models to assess effectiveness at each phase.*

Objective 4: *Identify potential interaction or mediation effects and assess such effects on primary outcomes.*

Exploratory Objective 5: *Implement a local innovation, IL ColonCARES Program, and assess its feasibility and effectiveness on the follow-up of abnormality.*

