2.2. Study Duration and Study Sites

The ACCSIS – Chicago UH3 Implementation Phase will last for four years (November 2019 to October 2023). In the UH3 Implementation Phase, we will have 4 clusters of clinics from four different FQHCs. Each cluster will have 5 to 12 clinics and a total of 20 to 35 primary care providers (internist, family practice physician, nurse practitioners, and physician assistants). Table 1 summarizes the characteristics of our FQHC partners. Together, our

Table 1: Characteristic of Partner Health Care Systems

	Total Patients	% of Racial Minority	% at or below 200% poverty	% of Uninsured	CRC Screening Rate	Adjusted Quartile Ranking on CRC Screening ¹	No. of Clinics ²	No. of Providers
PCC Community Wellness Center	48,357	92.2%	93.1%	9.3%	30.0%	Quartile 4	11	60
Aunt Martha's Youth Service Center, Inc.	51,343	80.9%	96.2%	16.5%	32.9%	Quartile 3	12	21
Lawndale Christian Health Center	51,235	96.9%	97.6%	30.2%	35.0%	Quartile 2	5	35
Near North Health Service Corporation	37,102	94.6%	97.3%	35.1%	31.0%	Quartile 3	7	20

1. Adjusted Quartile Ranking provides a health center's adjusted quartile ranking compared to health centers nationally for each of the clinical performance measures. Clinical performance for each measure is ranked from quartile 1 (highest 25% of reporting health center) to quartile 4 (lowest 25% of reporting health centers).

2. Reported by partner health care system.

partner FQHCs served 188,037 patients in 2016, and at least 10% of these patients were ≥ 50 years old. It is important to point out that three of our partners' CRC screening rates were in the lower third and fourth quartiles compared to other FQHCs in the nation, indicating room for improvement. We will continue to monitor their ranking throughout the study.

[figure not shown]

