3. STUDY DESIGN AND PROCEDURES

3.1 Study Design

We will use a stepped wedge cluster randomized trial design to assess the effectiveness of our proposed multilevel intervention. Although it will be preferable to use a traditional cluster-randomized trial to test our multicomponent, multilevel intervention, we will need a larger number of clusters, which will be more expensive and infeasible. Also, it is unacceptable for our partner(s) assigned to a control group to not benefit from well-studied evidence-based interventions. Since the stepped wedge design retains some elements of randomization and has the advantage for multiple data collection points over a long period and allows clusters to act as their own control, it is the best alternative to the gold standard.

In the UH3 Implementation phase, we will partner with four FQHCs. We will randomize the four FQHCs to either group 1 or group 2. The biostatistician will conduct the randomization independently from the research team. The difference between the two groups is that group 2 will start the implementation later. We will implement our multilevel intervention in three phases. In phase 1, we will implement the provider education and community outreach component. In phase 2, we will add the mobile patient reminder and the provider assessment and feedback components. In phase 3, we will add the CRC patient navigation component. Figure 1 shows our stepped wedge study design.

Figure 1: Stepped Wedge Study Design.

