3.5 Data Sources

During the first three months, we will work with the Quality Improvement Department at each partner site to collect baseline data on primary outcomes through the existing electronic medical record or chart reviews. After we start implementing the multilevel intervention, we will collect primary outcome data each quarter until the completion of the 4-year study period. Table 2 summarizes the primary outcome measures.

Table 2. Outcome Measures for the Multilevel Intervention

Outcome	Operational Definition	Data Sources	Data Collection Period	Level of Data Analysis
Patient CRC screening rates	Numerator: # of patients completed CRC screening Denominator: # of patients eligible for CRC screening	• EMR • Chart reviews as needed	Every quarter	Level 2, Level 3, Level 4
CRC ordering rates	Numerator: # of patients received order for CRC screening Denominator: # of patient eligible for CRC screening	• EMR • Chart reviews as needed	Every quarter	Level 2, Level 3, Level 4
Patient notification rates (FOBT/FIT +)	Numerator: # of patients notified Denominator: # of patients had FOBT/FIT +	• EMR • Chart review as needed	Every quarter	Level 2, Level 3, Level 4
Time to notification of positive results	# of days between notifying a patient with a positive result and the result available to the provider	• EMR • Chart reviews as needed	Every quarter	Level 2, Level 3, Level 4
Follow-up diagnostic evaluation referral rates	Numerator: # of patients received referral for evaluation Denominator: # of patients had FOBT/FIT +	• EMR • Chart reviews as needed	Every quarter	Level 2, Level 3, Level 4
Time to referral for follow-up diagnostic evaluation	# of days between the referral and the result available to the provider	• EMR • Chart reviews as needed	Every quarter	Level 2, Level 3, Level 4
Follow-up diagnostic evaluation completion rates	Numerator: # of patients completed diagnostic evaluation as ordered Denominator: # of diagnostic evaluation referral made	• EMR • Chart reviews as needed	Every quarter	Level 2, Level 3, Level 4
Time to completed diagnostic evaluation	# of days between the positive FOBT/FIT result available to the provider and the completion of the diagnostic evaluation	• EMR • Chart reviews as needed	Every quarter	Level 2, Level 3, Level 4

* Level 2 = Provider level; Level 3 = Clinic level; and Level 4 = organization level.

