4. DATA ANALYSES

In order to evaluate the effect of the multilevel, multicomponent intervention, we will take a step-by-step approach. First, each intervention effect at each time phase will be estimated separately using linear-mixed effects models. The estimate of intervention effect in each model will be used to test if additional intervention component significantly affects outcome measures. Next, we will develop a grand model including all three intervention effects simultaneously in addition to the models described above.

In this study, patients are nested within providers and providers are nested within clinics. The problem with nested data structures is that they violate the independence assumption of traditional regression models. Thus, we will use multilevel modeling to analyze our data. We will start with the unconditional three-level random intercept models:

$$\text{Level - 1: } Y_{ijk} = \beta_{0jk} + \epsilon_{ijk};$$

$$\text{Level - 2: } Y_{ijk} = \beta_{0k} + u_{jk} + \epsilon_{ijk}$$

$$\text{Level - 3: } Y_{ijk} = \beta_0 + v_k + u_{jk} + \epsilon_{ijk}$$

where Y_{ijk} is the observed outcome for patient i with provider j in clinic k . β_0 is the mean response across all clinic. v_k is the random effect of clinic k , u_{jk} is the random effect of provider j , and ϵ_{ijk} is the residual error. The random effects and residual errors are assumed independent of one another.

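### FQHCs are randomised, but the Section 4 models have no FQHC-by-time term and no small-sample inference at that level; FQHC-wide drift could make phase-effect standard errors too small, mainly for screening and ordering rates

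*Combined protocol and SAP*

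**What the plan says.** Section 2.2 states that "we will have 4 clusters of clinics from four different FQHCs". Section 3.1 makes the FQHC the unit of randomisation: "We will randomize the four FQHCs to either group 1 or group 2". It adds that "The difference between the two groups is that group 2 will start the implementation later".

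Section 4 starts the analysis at the phase level: "First, each intervention effect at each time phase will be estimated separately using linear-mixed effects models". Those estimates are used to test each added component, and a grand model with all three phase effects follows. The nesting is given as "In this study, patients are nested within providers and providers are nested within clinics". The equations contain a clinic effect, a provider effect and a residual, and "The random effects and residual errors are assumed independent of one another". The ICC step covers providers and clinics. Variances are estimated by REML, and the significance level is 0.05.

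Two other places point to a higher level. The Table 2 footnote in Section 3.5 reads "Level 2 = Provider level; Level 3 = Clinic level; and Level 4 = organization level", and the table lists all three levels for every outcome. Objective 3 in Section 2.1 promises a grand model for "primary outcomes within and across levels, as well as separate models to assess effectiveness at each phase". Section 4 contains no Level 4 equation.

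**The concern.** In a stepped wedge trial, the information on a phase effect comes from how outcomes change in units that have stepped, compared with units that have not yet done so. Here those units are four FQHCs in two groups. If one FQHC changes its EMR documentation, staffing or quality-improvement practice near its step, all of its clinics move together. A model with only clinic and provider intercepts treats that movement as many independent observations.

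Such change is plausible, though the documents do not quantify it. The components are delivered through each FQHC's own Quality Improvement Department (Section 3.2), and Section 3.2.1 attributes much low performance to incomplete recording of FIT results. A phase effect could then be called significant because one or two FQHCs changed for unrelated reasons.

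**Working it through.** The plan states no sample size, power, ICC or standard error, so there is no figure of its own to reproduce.

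**Inputs from the documents.** Table 1 of Section 2.2 gives 48,357 + 51,343 + 51,235 + 37,102 = 188,037 patients and 11 + 12 + 5 + 7 = 35 clinics. Its screening rates (30.0, 32.9, 35.0 and 31.0%) have a patient-weighted mean of 32.4% and an SD of 2.2 points. The text below it says at least 10% of patients are 50 or older. Objective 1 gives 6 months of baseline, or 2 quarters (Section 3.5 says three months). Four years is 16 quarters.

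**Assumptions not in the documents.** 10% of patients are eligible; all of them, or a quarter of them, are counted each quarter; the split is 2:2; group 2 lags by 2 or 4 quarters; phases last 3 or 4 quarters; quarter effects are in the model, although Section 4 shows none; FQHC-by-quarter shocks are independent, with SD 0.5, 1 or 2 points.

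**Step 1: sampling variance of one FQHC-quarter rate.** With all counted, the average n is 188,037 × 0.10 / 4 = 4,701. The variance is 0.324 × 0.676 / 4,701 = 0.466 points², an SD of 0.68 points. With a quarter counted it is four times as large, 1.86 points².

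**Step 2: actual SE divided by the model's SE.** Clinic intercepts and quarter effects remove constant differences and shared trend, so the ratio is approximately √(1 + s²/v), where s is the drift SD and v the sampling variance. Type I error is 2 × [1 − Φ(1.96/ratio)].

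| Drift SD (points) | All counted: ratio, type I error | A quarter counted: ratio, type I error |
|---|---|---|
| 0.5 | √(1 + 0.25/0.466) = 1.24, 11% | √(1 + 0.25/1.86) = 1.07, 6.6% |
| 1 | √(1 + 1/0.466) = 1.77, 27% | √(1 + 1/1.86) = 1.24, 11% |
| 2 | √(1 + 4/0.466) = 3.10, 53% | √(1 + 4/1.86) = 1.77, 27% |

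A full generalised least squares calculation with sandwich variance (35 clinics, unequal sizes, all 6 allocations) gives 11 / 26-27 / 52-53% and 6.5 / 11 / 25-27%. If drift is autocorrelated at 0.8 between quarters, the ratios at SD 1 are 1.93-2.12 (all) and 1.30-1.37 (a quarter), or 31-36% and 13-15%.

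**Step 3: the same patients recurring.** Section 4 has no patient effect across quarters. With exchangeable within-patient correlation ρ, the ratio is about √(1 − ρ + s²/v). With all counted and SD 0.5, ρ = 0.5 gives √(0.5 + 0.536) = 1.02, or 5.4%, and ρ = 0.8 gives 0.86, or 2.2%, which is no inflation. At SD 1 the ratios are 1.63 and 1.53, or 23% and 20%.

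**Step 4: sparse outcomes.** Suppose 1% or 0.2% of all patients enter the denominator each quarter, with the same rate as a stand-in. Then v = 4.66 or 23.3 points². SD 1 gives 7.5% or 5.5%, and SD 2 gives 15% or 7.0%. Drift of 5 points gives about 40-44% or 16-17%.

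**Step 5: other forms of FQHC variation.** Constant differences with SD 2.2 points give 5.1-8.2% in the grand model. Linear FQHC slopes (SD of the 4-year change 1-3 points) give ratios from 1.0 to 2.6, and with quarter effects some phase contrasts are almost unaffected.

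**Step 6: degrees of freedom and estimability.** Four FQHCs over 16 quarters give 64 FQHC-quarters. The grand model uses 4 FQHC + 15 quarter + 3 phase parameters, leaving 64 − 22 = 42. Suppose a separate model uses its phase and the preceding one. The count is then FQHC-quarters − (4 + quarters − 1 + 1). The smallest estimable case is phase 2 with lag 2 and phases of 3 quarters: 24 − (4 + 8) = 12. The largest is phase 3 with the same timing: 40 − (4 + 11) = 25. With a lag of 4, the separate phase 2 model is not estimable once FQHC and quarter effects are included. In every quarter where both groups contribute, group 1 is in phase 2 and group 2 in phase 1, so the phase term is aliased with FQHC.

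**Step 7: randomisation alone.** A 2:2 split has C(4,2) = 6 allocations, so the smallest two-sided randomisation p-value is 2/6 = 0.33.

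**The case against.** The equations are offered as starting points and examples, and Table 2 and Objective 3 suggest that an organisation level is intended. That is fair, but nothing later in Section 4 supplies the level. A plain FQHC intercept would not help either, because it does not capture drift.

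The size is open to dispute, and this part of the objection stands. With no drift, the plan's standard errors are not understated for this reason. The headline case counts every eligible patient each quarter for four years, so many patients recur; Step 3 then shows no inflation at SD 0.5, though 20-23% remains at SD 1. The calculation also gives the plan quarter effects that it does not show. Without them, a trend shared by all FQHCs would bias the phase effects, which is a separate problem. Six of the eight outcomes in Table 2 concern follow-up of a positive FOBT/FIT, where denominators are likely to be small. Time outcomes and the logistic outcome were not simulated.

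A reader might infer that the plan's p-values are shown to be invalid, or that the error rate is 50% or more. The documents support neither, because no figure in them selects a drift SD. A reader might also infer that 2-3 df is the only correct reference. It is the stricter choice: if only 2-3 df were available, a normal critical value would give 14-19% type I error. FQHC-quarter df are another defensible choice, and neither is an established correction for this design.

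**Conclusion.** The gap is real: the randomised unit does not appear in the Section 4 models, and Section 4 does not carry through the Level 4 listed in Table 2. The consequence is conditional. Drift shared by all clinics of an FQHC could make phase-effect standard errors too small, mainly for screening and ordering rates. On the assumptions above, type I error at a drift SD of 1 point is about 20-27% with all eligible patients counted, whether or not patients recur, and about 11% with a quarter counted and independent residuals. At SD 0.5 with all counted it is 11% with independent residuals and not inflated if patients recur. Inflation is small for sparse FOBT/FIT-positive outcomes unless drift is several points, and for some phase contrasts if drift is linear. This should be fixed; confidence in its size is medium.

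**What to change.** In Section 4:

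1. Include quarter effects, an FQHC effect and an FQHC-by-quarter random effect that allows correlation across quarters (AR(1) is one option), and keep the clinic and provider effects. Alternatively, analyse FQHC-by-quarter summaries with such correlation.
2. State which quarters each separate phase model uses, and prespecify a small-sample t or F reference at FQHC level. FQHC-quarter df (42 for the grand model, 12-25 for the estimable separate models under the timings assumed here) are one choice; 2-3 df is a stricter one.
3. Take phase 2 from the grand model if the lag is at least as long as phase 1.
4. Report a 2-df comparison of FQHC-level changes between the groups for phase 1 (four FQHCs minus two group means) as a robustness check.
5. Add FQHC to the ICC step, so that Section 4 agrees with Table 2.
6. State that with four FQHCs significance at 0.05 depends on the model, and that FQHC-level variances will be poorly estimated.

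The cost is SAP wording, some extra analysis and wider confidence intervals. At SD 1 point and autocorrelation 0.5, the phase 1 SE in the grand model rises from 0.42-0.53 to 0.80-0.92 points with all counted. On 42 df, the effect detectable with 80% power rises from 1.2-1.5 to 2.3-2.6 points. With a quarter counted it rises from 2.3-2.9 to 3.1-3.8 points. A 2-3 df reference would cost more, and the 2-df check needs an effect of about 6-7 points.

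The remedy is approximate. Simulation of the patient-level model gave type I error up to about 7%, but without the FQHC fixed effect, so that ceiling is not established for the model recommended here. The summary version gave about 7-9% under strong autocorrelation (0.8) with a lag of 4 quarters.

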The multilevel intervention components will include 1) provider education, 2) provider assessment and feedback, 3) patient reminder using mobile platform, 4) patient navigation, and 5) community outreach. The first three components will be implemented as part of the quality improvement project at the partner FQHCs. During the first six months, we will collect baseline data at our partner FQHCs. After we start implementing the multilevel intervention, we will collect outcome data every three months until the completion of the 4-year study period. At the clinic and provider levels, we will work with the Quality Improvement Department to collect outcome data on 1) CRC screening rates, 2) CRC screening order rates, 3) CRC screening completion rates, 4) follow-up diagnostic evaluation rates, 5) follow-up diagnostic evaluation completion rates, and 5) time to completion of diagnostic evaluation. At the patient level, we will collect data on patient navigation service utilization and the satisfaction of the services.

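### CRC screening and ordering rates are re-extracted every quarter, but the analysis model has no quarter index and no within-patient or clinic-by-quarter correlation, so phase-effect standard errors are generally wrong, in a direction the plan cannot foresee.

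*Combined protocol and SAP*

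**What the plan says.** On data collection, Section 3.5 states that "we will collect primary outcome data each quarter until the completion of the 4-year study period", and the opening summary says the same: "we will collect outcome data every three months until the completion of the 4-year study period". Section 3.1 justifies the stepped wedge partly because it "has the advantage for multiple data collection points over a long period and allows clusters to act as their own control". Table 2 in Section 3.5 defines the screening and ordering rates over all patients eligible for screening, every quarter, and lists provider, clinic and organization as the levels of analysis.

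On the model, Section 4 says that "each intervention effect at each time phase will be estimated separately using linear-mixed effects models", followed by a grand model. The stated hierarchy is that "patients are nested within providers and providers are nested within clinics". The response carries three indices, for the outcome that "is the observed outcome for patient i with provider j in clinic k", and "The random effects and residual errors are assumed independent of one another". Predictors may be added. One example, a cross-level interaction with age, also carries a provider random slope. No section gives a time index, a patient random effect, a residual covariance structure, robust standard errors, or a rule reducing each patient to one record.

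**The concern.** Section 4 itself warns that nested data break the independence assumption, and then omits the nesting that quarterly collection creates. A patient eligible in one quarter is usually eligible in the next, and screening status tends to carry over. Without a term for this, each patient-quarter record counts as new information once its provider and clinic are known.

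The phase effects answer Objective 3. If their standard errors are too small, an ineffective component may be declared effective; if too large, a real effect may be missed. Tests of patient characteristics that do not change over time are exposed in one direction only, towards false positives.

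**Working it through.** The plan states no sample size, ICC, standard error or within-patient correlation, so there is no design figure to reproduce. The check compares the standard error the model would report with the true one, under stated assumptions.

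**Inputs from the documents.** Four years of quarters: 4 × 4 = 16 at most. The baseline is six months in the summary ("During the first six months, we will collect baseline data at our partner FQHCs") but three months in Section 3.5, leaving 14 or 15 quarters after it. Partner table in Section 2.2: 11 + 12 + 5 + 7 = 35 clinics and 60 + 21 + 35 + 20 = 136 providers. Patients aged 50 or over: at least 10% of 188,037, about 18,804, or 138 per provider. Alpha is 0.05, taken as two-sided.

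**Assumptions.** The same patients are present in all 16 quarters. Group 1 is on intervention from quarter 3, and group 2 starts 6 to 12 months later. Within-patient correlation r is either constant or decays as AR(1).

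**Phase effect, simple on/off layout.** Let z be the on/off indicator after subtracting its clinic mean (and its quarter mean, if quarter terms are fitted), and R the within-patient correlation matrix. Then (true SE / reported SE)² = Σ z′Rz / Σ z′z, and the actual size of a 5% test is 2[1 − Φ(1.96 / ratio)].

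- Constant r: z sums to zero, so the ratio is √(1 − r). At r = 0.8, √0.2 = 0.45, and 1.96 / 0.45 = 4.4, so the size is about 0%.
- AR(1) 0.8, no quarter terms, 12-month lag: ratio 1.58; 1.96 / 1.58 = 1.24; size about 21%.
- AR(1), quarter terms, 12-month lag: the largest ratio is about 1.38, near r = 0.7; 1.96 / 1.38 = 1.42; size about 16%.
- AR(1), quarter terms, 6-month lag: 1.07 at r = 0.8 and 0.90 at r = 0.9, so the ratio crosses 1.

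**Phase effects, fuller layout.** This used 35 clinics, 136 providers, 138 patients per provider, three phase indicators four quarters apart, provider and clinic ICC of 0.02 each (assumed), and a lag of 2 or 4 quarters. Here the ratio is inverted, reported SE over true SE:

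| r | constant | AR(1) |
|---|---|---|
| 0.3 | 1.19–1.20 | 0.83–0.93 |
| 0.5 | 1.41 | 0.75–0.94 |
| 0.7 | 1.81–1.83 | 0.73–1.02 |

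The pattern is the same: a stable patient effect makes the reported standard error too large, and decaying correlation mostly makes it too small.

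**Patient-constant predictor, no provider random slope.** With T = 16, the understatement under constant r is √(1 + 15r). At r = 0.5 this is √8.5 = 2.92, and the size is about 50%. Under AR(1) it is √[1 + 2Σ(1 − k/16)rᵏ], k = 1 to 15. At r = 0.5 this is √2.75 = 1.66, and the size is about 24%.

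**Simulation.** A small run (24 providers, 15 patients each, 16 quarters, constant r = 0.5, 60 replicates) agreed in direction. Model SE against empirical SD was 0.0519 against 0.0403 for the intervention and 0.0133 against 0.0345 for a patient covariate. The AR(1) figures for the phase effects are analytic only.

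**Age-interaction example in Section 4.** A simulation with 136 providers, 138 patients each, 16 quarters, constant r = 0.5 and 1,500 runs included the provider random slope that the plan writes. Type I error was 5.2% for the interaction and 4.6% for age. Without the slope it was about 48% for both.

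**The case against.** The strongest reply is that patient-quarter records are an inference. The opening summary collects the screening outcomes at clinic and provider level, and Table 2 never lists the patient as a level of analysis. If provider-quarter or clinic-quarter rates are analysed, quarters within patient is not the missing level, and the provider and clinic intercepts already absorb constant correlation. This stands in part. Section 4 writes the outcome per patient, so the unit is unsettled. On the rate reading, the intercepts still cover only constant correlation, and quarter is still absent.

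A second reply is that six of the eight Table 2 outcomes follow a positive FOBT/FIT or a referral and normally give one record per event. So does the one binary patient-level outcome named in Section 4. This stands, and the point is limited to the screening and ordering rates.

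A third is that the sentence on independence strictly concerns random effects and residuals relative to one another. That is true, but no other residual structure is offered, so independent residuals are the natural reading.

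A reader might also infer that Objective 4's age interaction would be tested at a false-positive rate near 50%. The plan's own equation does not support this: its provider random slope absorbs the excess variation.

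**Conclusion.** The gap is real for the CRC screening and ordering rates. Fitted as written to patient-quarter records, the model reports phase-effect standard errors that are generally wrong. Under the assumed timing and correlations, true over reported runs from about 0.45 to about 1.6 (at most about 1.4 with quarter terms), giving a type I error of about 0% to 21%. Main effects of patient-constant predictors, without a provider random slope, have standard errors too small by 1.7 to 2.9 times at correlation 0.5.

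Two stronger readings should be resisted. One is that the phase-effect standard errors are always too small; constant correlation makes them too large. The other is that every plausible correlation pattern gives a materially wrong error bar; some AR(1) cases lie close to 1. The documents fix neither the correlation nor, in the text available, the phase dates, so the range shows sensitivity and is not a forecast. Sixteen quarters is a maximum. The plan should be corrected before analysis.

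**What to change.** In Section 4, state the unit of record for each Table 2 outcome, add a quarter index to the response, and include quarter fixed effects. Then:

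- For screening and ordering rates, either add a patient random intercept with AR(1) residuals to the provider and clinic intercepts, or analyse clinic-by-quarter counts with a clinic-by-quarter random effect in addition to the clinic intercept.
- For outcomes that follow a positive FOBT/FIT, use one record per positive result.

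The cost is SAP wording and a somewhat heavier model. The patient-level option could mean about 18,804 × 16 ≈ 301,000 records per outcome. It also requires that a patient keeps the same study number across extracts; Section 5.1 creates unique study numbers but does not say that they persist. The clinic-by-quarter option has at most 35 × 16 = 560 rows and needs no linkage, but it cannot test patient-level predictors.

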Adding predictor variables to the models is straightforward. For example, the level-3 random intercept and slope model with one predictor measured at each level is $Y_{ijk} = \beta_0 + \beta_1 X_{1ijk} + \beta_2 X_{2jk} + \beta_3 k + v_k + u_{jk} + \epsilon_{ijk}$, where $\beta_0 + \beta_1 X_{1ijk} + \beta_2 X_{2jk} + \beta_3 k$ is the fixed effect of the model and $v_k + u_{jk} + \epsilon_{ijk}$ is the random effect of the model. The fixed effect of the model specifies the overall mean relationship between the response and the predictor variables. The random effect of the model specifies how the provider and clinic specific relationships differ from the overall mean relationship. To assess the potential mediator effect, we will use the causal variable and the mediator variable as predictors in the model. To assess the cross-level interaction effects, we will add a product term to the model. For example, the model for a level-1 predictor (e.g. age) cross-level and interact with a level-2 predictor: $Y_{ijk} = \beta_0 + \beta_1 X_{1ijk} + \beta_2 X_{2jk} + \beta_3 (X_{1ijk} \bullet X_{2jk}) + u_{0jk} + u_{1jk} X_{1ijk} + \epsilon_{ijk}$. Since one of the patient-level (level-1) outcome measures is dichotomous (whether the patient adherence to follow-up diagnostic evaluation after a positive result within 9 months or not), we will add another level-1 model for the binary data:

$$\text{Level - 1: } \log [P_{ijk} / (1 - P_{ijk})] = \beta_{0jk} + \beta_1 X_{1jk}.$$

In this study, we will use the restricted maximum likelihood (**REML**) to estimate variances. REML treats the regression coefficients as unknown quantities to be estimated based on sample data and subtracts the needed degree of freedom when computing variance estimates. Since REML only allows for tests of models that differ in their variances, we will calculate the intraclass correlation (**ICC**) to access the variation in response variable across providers and across clinics prior to testing the models. At the end of the analysis, we will use the likelihood ratio test to

compare the nested models. The deviance values ($-2 \log L$) for the two models can be used to decide which model better fits the data:

$$(-2 \log L_{\text{Reduced Model}}) - (-2 \log L_{\text{Full Model}}) = \text{deviance}_{\text{Reduced Model}} - \text{deviance}_{\text{Full Model}}$$

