Statistical analyses will be conducted using Statistical Package for the Social Science (SPSS) version 23.0 and the significant level will set at alpha ≤ 0.05 .

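### Mediation is assessed with one outcome model that does not estimate or test an indirect effect, and the plan never links it to the other models that could supply one

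*Combined protocol and SAP*

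**What the plan says.** Section 2.1 makes mediation part of a numbered objective: "Identify potential interaction or mediation effects and assess such effects on primary outcomes". Only Objective 5 carries the label exploratory.

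Section 4 gives the whole mediation method in one sentence: "To assess the potential mediator effect, we will use the causal variable and the mediator variable as predictors in the model". The cross-level interaction method that follows it is written out as an equation; mediation is not.

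Three other parts of Section 4 bear on the point:

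- Phase-specific models: "First, each intervention effect at each time phase will be estimated separately using linear-mixed effects models". These are meant to test whether each added component changes the outcome measures.
- A combined model: "Next, we will develop a grand model including all three intervention effects simultaneously in addition to the models described above". No mediator is mentioned in it.
- A logit model for one dichotomous patient-level outcome, namely "whether the patient adherence to follow-up diagnostic evaluation after a positive result within 9 months or not".

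Table 2 in Section 3.5 lists ordering, notification and referral among the primary outcome measures, collected quarterly. Navigation use comes from navigator logs and is not in Table 2.

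The documents name no mediator and give no time order between mediator and outcome. They do not define an indirect effect, give no test or interval for one, and do not discuss mediator-outcome confounding.

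**The concern.** An indirect effect has two links: the intervention moves the mediator, and the mediator moves the outcome. An outcome model holding both the cause and the mediator shows only the second link, together with whatever effect of the cause remains. It does not show whether the intervention moved the mediator.

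An analyst following the sentence literally could therefore call any strong predictor of the outcome a mediator. The study combines several components and wants to know how they act. At stake is the answer to the mediation half of Objective 4: for example, whether a gain in screening came through more ordering, or a gain in follow-up through more referral.

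**Working it through.** The plan states no figure for mediation, so there is nothing to reproduce. The check is algebra, then a simulation under assumed values.

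**Algebra.** Take X as the intervention phase, M as the mediator and Y as the outcome. (Section 4 speaks only of a causal variable; that it means the intervention is my reading.) Let

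- M = aX + error
- Y = c'X + bM + error

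The planned model, Y on X and M, estimates c' (direct effect) and b (mediator-outcome slope). The indirect effect is a × b, and a does not appear in that model. In a linear model the total effect is c = c' + a × b, so c − c' = a × b, but this needs Y on X as a second model.

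**Simulation, linear case.** Assumed, not from the documents: c' = 0.2, 2,000 independent observations per run, 2,000 runs, and two-sided tests at 0.05. The plan says "the significant level will set at alpha ≤ 0.05" without stating sidedness. The joint test requires both a and b to be significant.

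| Truth | c' (planned model) | b (planned model) | b significant | c (Y on X) | c − c' | a × b | Joint test significant |
|---|---|---|---|---|---|---|---|
| a = 0, b = 0.4: no mediation | 0.201 | 0.400 | 100% | 0.201 | 0.000 | 0.000 | 5.1% |
| a = 0.5, b = 0.4: indirect 0.5 × 0.4 = 0.20 | 0.202 | 0.400 | 100% | 0.402 | 0.200 | 0.200 | 100% |
| a = 0.5, b = 0: no mediation | 0.200 | 0.000 | 5.1% | 0.200 | 0.000 | 0.000 | 5.1% |

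In the first two rows the planned model's output is the same to within 0.001, although mediation is absent in one and present in the other. Adding the mediator model separates them.

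**Simulation, logit case.** Assumed: 400,000 observations, a = 0 (so no mediation), intercept −0.5, c' = 0.5 and a standard normal mediator.

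| b | c without M | c' with M | c − c' |
|---|---|---|---|
| 0.5 | 0.467 | 0.493 | −0.027 |
| 1 | 0.418 | 0.508 | −0.089 |
| 2 | 0.305 | 0.499 | −0.194 |

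(Differences were taken before rounding.) The true indirect effect is 0 throughout. The coefficient still changes when the mediator enters, because odds ratios are non-collapsible. Comparing coefficients is therefore not a valid mediation check for the 9-month outcome.

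**Could the planned likelihood ratio test fill the gap?** Comparing models with and without M tests b, not a × b. The plan also states of its chosen estimation method: "Since REML only allows for tests of models that differ in their variances". Adding M changes the fixed effects, so by the plan's own account that comparison is not available under REML.

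**The case against.** The strongest reply is that the mediation sentence should not be read alone. Ordering, notification and referral are primary outcomes in Table 2, and Section 4 plans phase models for the outcome measures. A model of ordering on phase is therefore already planned, as is a model of the final outcome on phase. Suppose, purely for illustration, that the intervention raises ordering by 10 points, each extra order yields 0.6 completions, and the direct effect is 2 points. The planned analyses taken together would then report 10, 0.6, 2 and a total of 8. A reader could work out 10 × 0.6 = 6, or 8 − 2 = 6, by hand.

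This stands, and it rules out stronger readings. A reader might infer that the plan contains no model for the effect of the intervention on any mediator, or that Objective 4 cannot be answered at all. For the Table 2 mediators that is not so. A reader might also infer that a fully mediated effect would be reported as a null intervention effect, reversing the trial's conclusion. The documents do not support that either: the phase models are specified without a mediator, so a null coefficient after adding one would sit beside a non-null total effect.

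The reply does not supply the link. Nothing says that these models will be combined. The hand calculation has no interval or test. For a mediator outside Table 2, such as navigation use, no mediator model is stated. For the logit outcome, the subtraction fails.

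**Conclusion.** The point holds as an inadequate analysis rule for the mediation half of Objective 4. The one stated model gives c' and b but not a × b, and its mediator coefficient cannot distinguish mediation from its absence. The pieces for a proper analysis are partly planned but unlinked, and no indirect effect is defined, estimated or tested.

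The algebra does not depend on the assumed values. The simulated sizes do: they use independent observations and chosen coefficients, so they show what the model can identify, not what this trial would find. Even c' is a direct effect only if there is no unmeasured mediator-outcome confounding, which the plan does not address.

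The reach is limited to Objective 4. The effectiveness analysis under Objective 3 is not affected. The change should be made, but the trial's main result does not depend on it.

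**What to change.** Replace the mediation sentence in Section 4 with a linked set of multilevel models sharing the same random effects and the same adjustment for time: (1) outcome on phase, (2) mediator on phase, (3) outcome on phase plus mediator. Then:

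- Name the mediators, for example ordering or referral, and navigation use if intended. Measure each before the outcome it is meant to explain; allowing the same quarter does not by itself secure that order.
- Define and report the indirect effect: product of coefficients for linear outcomes, and a counterfactual mediation estimator for the binary 9-month outcome.
- Give an interval that keeps the clustering, for example Monte Carlo or a cluster bootstrap. State that it may be too narrow because only four FQHCs are randomized (Section 3.1). Resampling clinics alone does not reflect that level.
- Adjust for measured mediator-outcome confounders and state the assumption of no unmeasured ones.
- Label the mediation result exploratory.

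The cost is new SAP wording and a modest amount of extra analysis. Ordering, notification and referral data, and navigator logs, are already to be collected. The interval for the indirect effect will be wider than those for the single coefficients now planned.
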